#### **9.5.3            Analyses of Exploratory Efficacy Endpoint(s)**

## **9.6 Safety Analyses**

### **9.6.1 Analyses of Primary Safety Endpoint(s)**

All analyses of safety endpoints will be performed using the Safety Analysis Set according to the actual treatment received.

### **9.6.2 Adverse Events**

The Medical Dictionary for Regulatory Activities (MedDRA) version at the time of data base lock will be used to code all adverse events (AEs).

Subject incidence of all treatment-emergent adverse events, serious adverse events, adverse events leading to withdrawal of investigational product, and fatal adverse events will be tabulated by system organ class and preferred term in alphabetical order by treatment group.

Subject incidence of events of interest (standardized MedDRA queries and/or Amgen customized queries) will also be summarized according to their categories and preferred term by treatment group.

In addition, summaries of treatment-emergent and serious adverse events by preferred term will be provided in descending order of frequency in etelcalcetide arm.

Summaries of treatment-emergent and serious adverse events will be tabulated by system organ class, preferred term, and severity by treatment group.

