6.2.3.3 Symptomatic Hypocalcemia

The clinical signs and symptoms of hypocalcemia include increased neuromuscular excitability, manifested as paresthesias of the fingers, toes, and circumoral region. In more extreme cases, there may be muscle cramping, carpopedal spasm, laryngospasm, and seizures. Symptoms reflect not only the degree of hypocalcemia, but also the acuteness of the fall in serum calcium concentration. Signs of latent tetany include Chvostek's sign (twitching of the upper lip after tapping on the facial nerve below the zygomatic arch) and Trousseau's sign (carpal spasm after inflating a cuff on the upper arm above systolic blood pressure for 2 to 3 minutes). Various mental disturbances, such as irritability, depression, and even psychosis, have been attributed to hypocalcemia. Cardiac effects of hypocalcemia include a prolonged QT interval and, rarely, ventricular tachyarrhythmia's or congestive heart failure which may be fatal.

Common symptoms of hypocalcemia include paresthesias (fingertips, toes, or perioral), fatigue, muscle cramps, irritability or anxiety, tetany (eg, carpopedal spasm, laryngospasm), Chvostek's sign, seizures, and prolonged QT interval.

If symptomatic hypocalcemia is suspected, calcium levels should be closely monitored, and corrective measures should be undertaken by the Investigator. Calcium supplementation can be provided by IV infusion (eg, a calcium gluconate) and/or oral calcium supplementation.

Suppressed levels of serum magnesium can be associated with refractory hypocalcemia. Serum magnesium should be closely monitored in subjects with hypocalcemia, and magnesium supplements should be provided as needed.

If dosing with IP is suspended for symptomatic hypocalcemia, dosing may resume at a lower dose once symptomatic hypocalcemia has resolved when the central laboratory cCa ≥ 8.3 mg/dL (2.07 mmol/L), and once the Investigator has notified the IVR/IWR.

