	18	19	20	21	22	23	24	25	26	27 ^b			
IV investigational product administration				Three times per week at the end of the hemodialysis session ending at week 26									
Dose titration ^c													
Informed Consent													
Inclusion/ Exclusion													
Medical History													
Demographics													
Prior & Concomitant Medication	X	X	X	X	X	X	X	X	X	X	X	X	
Physical Examination											X	X	
Randomization													
Dispensation of oral IP bottle				X				X					
Pill count	X		X		X		X	X	X			X	
TIW Admin of IV IP (by site staff at the end of hemodialysis) ^d	X	X	X	X	X	X	X	X	X				
Adverse events ^e	X	X	X	X	X	X	X	X	X	X	X	X	
Vital status ^f									X			X	
Prior to dialysis													
ECG ^g										X		X	
Serum pregnancy test ^h						X					X	X	
Hematology											X	X	
Chemistry											X	X	
Albumin, Ca ^{ij}	X		X		X		X		X	X			X ^d
Phosphorus			X			X		X	X				
PTH	X	X	X		X		X		X	X	X	X	
PK ^k								X		X			
25(OH)D													
ADA											X	X	
After dialysis													
Pulse and blood pressure ^L									X			X	
Height													
Weight									X			X	
PK (10-30 min post dose) ^{ik}							X						

Footnotes defined on the next page

Approved

ADA = antidrug antibody; [REDACTED]; cCa = correct calcium; Ca = calcium; [REDACTED]; ECG = electrocardiogram;

IP = investigational product; IV = intravenous; PTH = parathyroid hormone, PK = pharmacokinetic; TIW = three times per week

^a Assessments during the Treatment Period should be performed during the designated study week on the same hemodialysis treatment day of the week as the day dosing was started whenever possible.

^b Week 27 assessments should be performed on the day of the first hemodialysis treatment after the last dose of IP.

^c The dose of IP may be decreased at any time.

^d When dosing with IP is suspended for cCa < 7.5 mg/dL (**1.87 mmol87mmol/L**), a predialysis serum sample for albumin and calcium should be submitted to the central laboratory on the day dosing is suspended. Dose suspension samples do not need to be collected if a routine, local chemistry or albumin/calcium/P sample is obtained on the same day.

^e After informed consent and before first dose of IP, only serious adverse events are to be reported. Subjects will be followed for both adverse events and serious adverse events for 30 days after the last dose of IP.

^f Vital status will only be appropriately ascertained by sites for subjects who early terminated the study.

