7.3.12 Vital Status

Vital status must be obtained for all subjects within the limits of local law. This includes subjects who may have discontinued study visits with or without withdrawing consent and should include interrogation of public databases, if necessary. If deceased, the date should be obtained.

For any subject who terminates early, study sites will be expected to attempt to collect survival status at week 26, if appropriate based on the applicable local regulations.

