8.3 Reasons for Removal From Procedures, Treatment, or Study

8.3.1 Reasons for Removal From Treatment

Reasons for removal from protocol-required IP(s) or procedural assessments include any of the following:

- **Protocol Specified Criteria**
 - subject requires a significant permanent change in hemodialysis prescription to maintain adequate hemodialysis
 - subject receives a kidney transplant
 - subject undergoes a parathyroidectomy
- **Ineligibility determined**
- **Protocol deviation**
- **Noncompliance**
- Subject request
- **Adverse event**
- Death
- Lost to follow-up
- Decision by Sponsor (other than subject request, safety concern, lost to follow-up)

Approved

Subjects who are removed from protocol-required IP(s) will be approached by investigators to determine the amount of follow-up assessments but at a minimum for vital status at the week 26.

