### Treatment Emergent Adverse Events (TEAE)

Adverse events (AEs) starting on or after the Study Day 1 as determined by the flag indicating if the adverse event started prior to the first dose of IP on the Adverse Events Summary CRF and up to 30 days after the last dose date. Serious adverse events (SAEs) starting on or after the Study Day 1 as determined by the flag indicating if the adverse event started prior to the first dose of IP on the Adverse Events Summary CRF and up to 30 days after the last dose date.

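### Week-26 vital status is collected for subjects who stop early, but no readable SAP output uses it, so some deaths after study exit would appear in no table

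*SAP*

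**What the plan says.** **Collection of survival data.** Protocol 7.3.12 states: "Vital status must be obtained for all subjects within the limits of local law". It includes subjects who stopped visits, with or without withdrawing consent, and allows public databases to be consulted. For early terminators it adds that "study sites will be expected to attempt to collect survival status at week 26, if appropriate based on the applicable local regulations". Protocol 8.3.1 makes this the least that is sought after removal from treatment: "but at a minimum for vital status at the week 26". The schedule in 7.1 has a vital-status row at week 26 and at early termination, with a footnote that narrows it: "Vital status will only be appropriately ascertained by sites for subjects who early terminated the study". Protocol 12.4 permits a search of public records for survival where allowed.

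**Adverse event collection.** Adverse events and serious adverse events are recorded to 30 days after the last dose (Protocol 7.3.10, 9.2.1.1, 9.2.1.2). Protocol 9.2.1.3 imposes no duty to monitor for later serious events. The SAP definition of treatment-emergent events (5.3) covers events that start "up to 30 days after the last dose date".

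**Reporting of deaths.** SAP 9.6.2 tabulates "adverse events leading to withdrawal of investigational product, and fatal adverse events" by arm. SAP 9.2 summarises reasons for study and treatment discontinuation by randomised arm on the FAS, and death is a listed reason (Protocol 8.3.1, 8.3.2). The readable SAP mentions neither vital status nor survival status. SAP section 10 declares no changes from the protocol's analyses.

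**The concern.** The protocol sets up a route for learning of deaths in subjects who are no longer being seen, and the SAP has no output for what that route finds. The two outputs that count deaths both depend on how long a subject was treated or stayed in the study. Stopping treatment happens after randomisation, can differ by arm, and may mark clinical deterioration. A fatal-event count whose follow-up ends 30 days after the last dose therefore compares arms over unequal periods, and the end of follow-up may be related to risk.

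The protocol's own safety rationale makes this relevant. Section 6.2.3.3 describes cardiac effects of hypocalcemia, including "ventricular tachyarrhythmia's or congestive heart failure which may be fatal", and 9.2.2 lists cardiac failure and ventricular arrhythmia as events of interest. In the earlier head-to-head study, symptomatic hypocalcemia was reported in 5.0% of etelcalcetide subjects and 2.3% of cinacalcet subjects (Protocol 2.2.1). SAP 8.4 recognises differential dropout as a source of bias but plans to explore it only for the primary and secondary endpoints. At stake is an undercount of deaths that could be uneven between arms.

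**Working it through.** **Step 1. Which deaths by week 26 reach a table?**

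| Situation | Fatal adverse event table | Discontinuation-reason table |
|---|---|---|
| Event starts within 30 days of last dose, death at any later time | Yes, because reported events are followed until they stabilise or resolve (Protocol 9.2.1.1, 9.2.1.2) | If still in the study |
| Event starts later, subject still in the study at death | Not normally collected | Yes, as death |
| Event starts later, subject already withdrawn, lost, or ended at the 30-day visit | Not normally collected | No; the earlier end-of-study status stands |

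Only the third row is lost. It is a real category: the 30-day visit is the end-of-study visit (Protocol 3.5.1), and subjects who stop early are also asked to attend it (7.2.4, 7.2.5). These are the subjects for whom week-26 vital status adds information.

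**Step 2. How much time is uncovered?** The documents give no mortality figure, so there is no figure of the plan's own to reproduce.

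Inputs from the documents: 26 weeks of treatment = 26 × 7 = 182 days; a 30-day collection window; 660 subjects; 10% dropout (SAP 3.2). Assumptions: last-dose days of early stoppers spread evenly over 0-182; annual mortality of 5%, 10% or 15%; and 20% stopping as an alternative.

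- Uncovered days before week 26 = max(0, 182 − (last-dose day + 30)). This gives 124 days for a stop at week 4, 68 at week 12, 12 at week 20, and 0 for a last dose on or after day 152.
- Share of early stoppers with any gap = 152/182 = 84%.
- Mean gap per early stopper = (152²/2)/182 = 63.5 days.
- Total person-time to week 26 = 660 × 182/365.25 = 329 person-years.
- Uncovered at 10% stopping = 66 × 63.5/365.25 = 11.5 person-years (3.5% of 329).
- Uncovered at 20% stopping = 132 × 63.5/365.25 = 22.9 person-years (7.0%).

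**Step 3. Expected deaths in the gap, both arms together.**

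- If the 10% are all alive when they stop: 11.5 × 0.05, 0.10, 0.15 = 0.6, 1.1, 1.7.
- At 20% stopping, on the same basis: 1.1, 2.3, 3.4.
- If the 10% includes deaths: total deaths to week 26 are about 329 × 0.05, 0.10, 0.15 = 16, 33, 49. Treating these as deaths on treatment leaves 66 − 16 = 50, 66 − 33 = 33 and 66 − 49 = 17 stoppers who are alive. Their uncovered time is 50, 33 and 17 × 63.5/365.25 = 8.7, 5.7 and 3.0 person-years. Expected deaths are 8.7 × 0.05, 5.7 × 0.10 and 3.0 × 0.15 = 0.4, 0.6 and 0.4.

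The range at 10% stopping is therefore about 0.4 to 1.7.

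**Step 4. Direction of the remaining error.** Three features make these figures too high: the first two rows of the table in step 1 are counted elsewhere, and SAP 5.1 counts a zero dose as a dose, which can push the last-dose date later for suspended subjects. Mortality that rises after stopping would make them too low.

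**The case against.** A reader might infer that every death more than 30 days after the last dose drops out. The documents do not support that. The SAP's 30-day limit is on event onset, not date of death, and SAP 9.6.2 does not clearly apply the treatment-emergent restriction to fatal events at all. The limit comes mainly from the collection window, and events reported within it are followed further. Deaths in subjects still in the study appear as a discontinuation reason.

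A reader might also infer that a planned death comparison is being cut short. None is planned. Mortality is not an endpoint in the readable text, and Protocol 10.5.4 asks for a table of fatal adverse events without formal testing, which SAP 9.6.2 supplies. The SAP does not fail to carry out a protocol analysis.

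Nor is week-26 status guaranteed for every early stopper. It is an expected attempt, limited by local law, so the data may be incomplete. Finally, the contents list shows appendix pages ahead of SAP Appendix C that are not in the readable text, and some sections are redacted, so the absence of any output can be stated only for what can be read.

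All of this stands and narrows the point. It does not remove it: vital status is sought for subjects who have already left the study, and neither table that counts deaths can show what it finds.

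**Conclusion.** The point holds in a limited form. Deaths by week 26 from later-onset events, in subjects who had already left the study, would be reported in no readable SAP output, and follow-up for fatal events varies with the time of stopping. The expected number is small, about 0.4 to 1.7 over both arms at 10% stopping, and rests on the even stop times and 5-15% annual mortality assumed above. It may differ by arm, and where the difference in deaths between arms is itself small, one or two deaths could change how the table reads. No efficacy conclusion or protocol-specified test is affected. This is a worthwhile, inexpensive reporting change and does not touch clinical management.

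**What to change.** Add to SAP 9.6.2 one descriptive table of all-cause deaths from randomisation to week 26, by randomised arm on the FAS. Count deaths from any source (fatal adverse event, end-of-study page, vital status) whatever the time since last dose. Give number, percent and the number with unknown vital status in each arm. A between-arm difference with a 95% confidence interval is optional and descriptive, without a formal test. Keep the fatal adverse event table on the Safety Analysis Set unchanged.

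The cost is a sentence in the SAP and one table from data the protocol already collects. The table departs from the SAP's convention of reporting safety on the Safety Analysis Set, so the text should say why the FAS is used. It will include deaths remote from treatment, and vital status may be incomplete. It should therefore be labelled all-cause and read beside the fatal adverse event table.

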### **9.6.3 Laboratory Test Results**

Laboratory values below the parameter-specific the lower limit of quantification (LLOQ) or above the parameter-specific upper limit of quantification (ULOQ) will be imputed as the LLOQ or ULOQ value, respectively.

In this section, cCa refers to cCa measured by central laboratory, Ca refers to Ca measured by central laboratory. All cCa and Ca results from local laboratory testing will be excluded from analysis.

Laboratory parameters including corrected calcium, PTH, P and Ca x P will be summarized by treatment group and the protocol-specified scheduled visit. Summaries of the absolute value change from baseline, and percent change from baseline will also be provided.

Shift tables will be provided for albumin, corrected calcium, potassium, phosphorus, magnesium, hemoglobin, alkaline phosphatase (ALP), alanine aminotransferase (ALT), aspartate aminotransferase (AST), total bilirubin (TBL) by summarizing the most

---

extreme changes in toxicity grade from baseline (increase and/or decrease as appropriate) to any visit during the study while the subjects are receiving IP. The toxicity grading will be based on common terminology criteria for adverse events (CTCAE) version 4.0.

Number and percentage (with 95% confidence interval) of subjects with low calcium as defined by cCa < 7.0 mg/dL, < 7.5 mg/dL, < 8.0 mg/dL, < 8.3 mg/dL, 7.0 - < 7.5 mg/dL, and 7.5 - < 8.3 mg/dL during the study will be summarized by treatment group. Each subject's lowest corrected calcium value during the study (post-baseline) will be used in this analysis.

Number and percentage of subjects with 2 consecutively low corrected calcium, defined by 2 consecutive post-baseline corrected calcium < 7.5 mg/dL, < 8.0 mg/dL and < 8.3 mg/dL during the study will be summarized by treatment group.

A summary of potential Hy's law cases meeting lab criteria will be provided. Subject incidence meeting the following criteria will be provided at baseline and post-baseline:

ALT or AST > 3 x ULN and TBL  $\geq$  2 x ULN and ALP < 2 x ULN within  $\pm$  7 days  
For subjects who meet the Hy's law lab criteria, information on their medical history and concomitant medication will be provided to further evaluate whether these are true Hy's law cases.

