Safety 
 
To assess the safety and tolerability of etelcalcetide compared to cinacalcet
 
To evaluate antibody formation to etelcalcetide
 
	
 
Incidence of cCa < 8.3 mg/dL measured by the central laboratory at any time during the study
 
Incidence of cCa < 8.0 mg/dL measured by the central laboratory at any time during the study
 
Incidence of cCa < 7.5 mg/dL measured by the central laboratory at any time during the study
 
Incidence of treatment-emergent symptomatic hypocalcemia during the study
 
Incidence of antibody formation to etelcalcetide
 
Nature, frequency, severity, and relationship of treatment-emergent adverse events
 

Exploratory 

	

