#### Corrected Total Serum Calcium (cCa)

$$\text{Corrected calcium (mg/dL)} = \text{Total calcium (mg/dL)} + (4 - \text{albumin [g/dL]}) \times 0.8$$

Total serum calcium will be corrected using above formulae if the serum albumin is < 4 g/dL or 40 g/L, otherwise cCa equals total serum calcium.

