### Low Calcium Based on Corrected Calcium Values

cCa values measured by central laboratory will be used to identify cases of low calcium of different severities using the following three categories:

< 7.0 mg/dL, 7.0 - < 7.5 mg/dL, and 7.5 - < 8.3 mg/dL.

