## **9. Statistical Methods of Analysis**

### **9.1 General Considerations**

This is a phase 3 study to evaluate the efficacy of etelcalcetide as compared to cinacalcet. The primary objective is to determine if etelcalcetide is non-inferior to cinacalcet on achievement of a > 30% reduction from baseline in mean predialysis serum PTH during the EAP. Etelcalcetide will be considered non-inferior if the upper

bound of the two-sided 95% CI of the treatment difference (cinacalcet – etelcalcetide) is smaller than 12%. If this criterion is met, the 2 key secondary endpoints will be tested sequentially. The testing for the endpoint of achievement of a > 50% reduction from baseline in mean predialysis serum PTH during the EAP will be carried out first. Only if the result achieves statistical significance, the secondary endpoint of achievement of a > 30% reduction from baseline in mean predialysis serum PTH during the EAP will be tested. The other secondary endpoints will be formally tested for superiority if both key secondary endpoints are statistically significant. To control for the family-wise error rate, the Hochberg procedure of adjustment for multiple comparisons will be used for testing of the other secondary endpoints. The primary analysis of all primary and secondary endpoints will be conducted on the FAS.

For the efficacy endpoints using laboratory measurements (predialysis PTH, cCa, and P), values based on averaging over the EAP will be used in the analyses where applicable.

Baseline values for PTH, cCa, and P will be based on the mean of the last screening value and the day 1 value.

For analyses performed on cCa and Ca, only central laboratory results will be used.

Descriptive statistics include number of observations (n), mean, standard deviation (SD) or standard error (SE), median, 1st (Q1) and 3rd (Q3) quartiles, minimum and maximum will be used to summarize continuous variables. The number and percent of subjects will be used to summarize the categorical variables.

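### A cheap improvement, not an error: add one supplementary either-laboratory corrected-calcium table, because the central-only threshold rows cannot show subjects whose only low value was local

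*SAP*

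**What the plan says.** The central-only rule is deliberate and consistent. SAP 2.1 defines the three incidence endpoints (cCa < 8.3, < 8.0 and < 7.5 mg/dL) as "measured by the central laboratory at any time during the study", matching Protocol 10.1.1.4. SAP 5.3 repeats it for the severity bands: "cCa values measured by central laboratory will be used to identify cases of low calcium of different severities using the following three categories". SAP 9.1 makes it general: "For analyses performed on cCa and Ca, only central laboratory results will be used". SAP 9.6.3 then closes off local data: "All cCa and Ca results from local laboratory testing will be excluded from analysis". For the threshold rows, "Each subject's lowest corrected calcium value during the study (post-baseline) will be used in this analysis", and in that section cCa means the central measurement.

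The protocol gives local cCa a real part in safety management. Sections 6.2.3.2 and 6.2.5 allow it for safety concerns and suspension, require suspension when it is below 7.5 mg/dL, and forbid collecting local and central cCa together. Section 6.2.5 requires all local cCa results on the eCRF. Section 9.2.3 brings those collected for safety concerns into the clinical database.

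**The concern.** The local sample is drawn because someone is worried, so it may be the sample that catches the low point. By the time a central sample is taken, dosing has been suspended and calcium measures are permitted. The threshold rows use the lowest central value, so a dip seen only locally leaves no mark on them. Hypocalcemia is a listed event of interest (Protocol 9.2.2). A reader of the planned tables could not tell how many subjects in each arm crossed a threshold only at the local laboratory, including those whose dosing was suspended for it.

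**Working it through.** No stated figure is in dispute, so there is none to reproduce. The check traces one kind of subject through the rules and then looks for another planned output that would show them.

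**Step 1: how a subject falls out of a row.** Take a subject with a local cCa < 7.5 mg/dL.
- Same time: no central cCa may be collected with the local one (Protocol 6.2.5).
- Day of suspension: a central sample is to be sent, but it is waived if a routine local sample is obtained that day (Protocol 7.4; Tables 2 and 3, footnote d).
- Next dialysis session after notification: a confirmatory central sample is drawn, with dosing suspended (Protocol 6.2.3.2).

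Let m be the lowest of all the subject's post-baseline central values.
- m < 7.5: counted in every row that applies.
- 7.5 ≤ m < 8.0: missing from the < 7.5 row.
- 8.0 ≤ m < 8.3: missing from the < 7.5 and < 8.0 rows.
- m ≥ 8.3: in no row.

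A local value from 7.5 to < 8.3 without symptoms triggers no mandatory central draw, so the next central value may simply be the next scheduled one.

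**Step 2: direction.** The minimum over both laboratories cannot exceed the central minimum. Cumulative rows (below a threshold) built on either laboratory can therefore only equal or exceed the central-only rows. Banded rows (7.0 to < 7.5, 7.5 to < 8.3) could move either way, because a subject may drop to a lower band. Cumulative thresholds are thus the clean comparison.

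**Step 3: do other outputs supply the count?**
- Shift tables (SAP 9.6.3) are also central-only, use toxicity grades, and run "to any visit during the study while the subjects are receiving IP".
- Events of interest "will also be summarized according to their categories and preferred term by treatment group" (SAP 9.6.2). One reported term, for decreased blood calcium, covers both any asymptomatic value < 7.5 and clinically significant values of 7.5 to < 8.3 (Protocol 9.1.1, 9.2.3). The reporting rule has no cut at 8.0, so the thresholds cannot be separated.
- A suspension for a local cCa < 7.5 is registered as a product-related adverse event or symptomatic hypocalcemia (Protocol 6.2.5). That registered reason does not isolate these subjects. The eCRF also records a reason (Protocol 6.2.3); its categories are not visible here.

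**Step 4: scale.** With 330 planned per arm (SAP 3.2), one local-only subject is 100 × 1/330 = 0.30 points. For assumed counts of 5, 10 and 20: 100 × 5/330 = 1.5, 100 × 10/330 = 3.0 and 100 × 20/330 = 6.1 points. These counts are assumptions to show scale; the documents give no basis for choosing among them.

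**The case against.** The strongest reply is that nothing is broken. Central measurement is the defined endpoint, standardizing laboratory source was the main stated reason for Amendment 3, and safety results are descriptive with no formal testing (Protocol 10.5.4). All of that stands. A reader might infer that the SAP contradicts the protocol or misapplies the endpoint; the documents show the opposite.

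The second reply is that the important cases are already reported. Any asymptomatic cCa < 7.5 and any symptomatic fall below 8.3, from either laboratory, must be recorded as an adverse event (Protocol 9.1.1). This also stands. A reader might infer that local lows disappear from the safety report; they do not. At < 7.5 only the threshold label is lost. The values that can go wholly untabulated are asymptomatic local results of 7.5 to < 8.3 not judged clinically significant.

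Third, central sampling is frequent: albumin and calcium about every two weeks through weeks 26 and 27 (Tables 2 and 3), suspension-day samples unless waived, and confirmatory, weekly and unscheduled draws (Protocol 6.2.3.2). Persistent hypocalcemia should be caught. The gap is confined to transient lows.

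Fourth, local data are uneven. Assays are not standardized across about 120 centers and testing is prompted by safety concerns. Protocol 7.4 also says that results of the testing it describes are kept in site source documents, which sits awkwardly with the requirement in 6.2.5 to put all local cCa on the eCRF. This limits what the table can show and is why it must be supplementary.

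**Conclusion.** The point holds as a worthwhile, low-cost addition. The central-only rows are correct for the endpoint but can count a subject suspended for a local cCa < 7.5 mg/dL as having no event at that threshold, and no planned output shown in the SAP recovers that number.

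Its size is unknown: 0.30 points per subject on 330, slightly more if the Safety Analysis Set is smaller than 330 per arm. Nothing in the documents supports a claim that the undercount is large or that it differs between arms. Equally, a local-only count of zero would not prove the central rows complete, since only subjects with a local test can contribute and testing is selective. No inferential result, endpoint definition or dosing rule is affected. The conclusion assumes that local cCa results are entered as Protocol 6.2.5 requires.

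**What to change.** Keep the central-only rule for every existing output: endpoint rows, the < 7.0 and banded rows, two-consecutive rows, by-visit summaries and shift tables. Add one stated exception to the central-only sentences in SAP 9.1 and 9.6.3, for a descriptive table labeled supplementary, by arm, on the Safety Analysis Set:

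- for each of < 8.3, < 8.0, < 7.5 and < 7.0 mg/dL, the number and percentage of subjects with a post-baseline cCa below the threshold from either laboratory;
- for each threshold, the number whose only such value was local;
- the number of subjects with any local cCa, so that the counts can be read against how often local testing was done.

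Convert local results to mg/dL. Where local albumin is available, apply the SAP 5.3 rule ("Total serum calcium will be corrected using above formulae if the serum albumin is < 4 g/dL or 40 g/L"). Where only a reported local cCa exists, use it and footnote how many subjects this affects. Add a note that assays are unstandardized and testing is safety-triggered, and that a zero local-only count does not establish completeness. Before database lock, confirm that local cCa was entered on the eCRF, given the source-document wording in Protocol 7.4.

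The cost is one table and its programming. If Protocol 6.2.5 has been followed, no new data collection is needed.
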